6.1.2. General Considerations for Analyses during Period 2 (Induction Dosing Period)

Period 2 starts after the first dose of study treatment (Visit 2, Week 0) and ends prior to the first injection of study treatment at Week 12 (Visit 7) or the early discontinuation visit (between Weeks 0 and 12). If a patient has Visit 7 but does not receive injection at Week 12 (Visit 7), the last recorded time for Visit 7 is used as the end time for Period 2.

Baseline for ITT and Safety Populations will be defined as the last available value before the first injection for efficacy, health outcomes, and safety analyses. In most cases, this will be the measure recorded at Week 0 (Visit 2). For efficacy/health outcome measures, if the patient does not take any injection, the last available value on or prior to randomization date will be used. Change from baseline (CFB) will be calculated as the visit value of interest minus the baseline value. For safety analyses using a baseline period, the baseline period is defined as the time from Visit 1 to the date/time of the first injection.

Comparisons between each ixekizumab treatment group (80 mg Q2W or 80 mg Q4W) and placebo will be performed for all analyses in Period 2.

The primary analysis method for treatment comparisons of categorical efficacy and health outcomes variables will be a logistic regression analysis with treatment as a factor using PROC Logistic. The odds ratio and the corresponding 95% CIs, as well as the treatment differences and the corresponding 95% CIs, will be reported. Secondary analysis will be conducted using a Fisher's exact test. In the case when logistic regression model does not produce statistical results due to sparse data, Fisher's exact test will be used.

For all categorical efficacy and health outcome variables that are collected at repeated visits, treatment group comparisons will be analyzed at each visit using the logistic regression model. Missing data will be imputed using the NRI method (Section 6.2.1).

As a sensitivity analysis for selected categorical efficacy measures e.g. sPGA (0,1), sPGA (0), PASI 75/90/100, a categorical, pseudo-likelihood based mixed-effects model of repeated measures (categorical mixed-effects model of repeated measures [MMRM]) estimating the percentage of patients achieving response across postbaseline visits will be used. The model will include treatment, baseline value, visit, treatment-by-visit and baseline-by-visit interactions as fixed factors. The binomial distribution and the logit link function will be used. The restricted maximum likelihood (REML) will be used. An unstructured covariance matrix will be used to model the within-patient variance-covariance errors. The Kenward-Roger approximation will be used to estimate the denominator degrees of freedom. The Newton-Raphson with ridging optimization technique will be used to aid with convergence. The probability of response, the corresponding 2-sided 95% CI, and the p-value for treatment comparisons at Week 12 (Visit 7) and all other postbaseline visits will be reported.

The primary analyses for the continuous efficacy and health outcomes variables will be made using mixed effects for repeated measures (MMRM) analysis. A secondary analysis for selected continuous efficacy and health outcomes variables will be made using analysis of covariance (ANCOVA).

When the MMRM model is used, the model will include treatment, baseline value, visit, treatment-by-visit, and baseline-by-visit interactions as fixed factors. The covariance structure to model the within-patient errors will be unstructured. If the unstructured covariance matrix results in a lack of convergence, the heterogeneous Toeplitz covariance structure, followed by the heterogeneous autoregressive covariance structure, followed by the compound symmetry will be used. This order is specified according to a decreasing number of covariance parameters in the structure. The REML will be used. The Kenward-Roger method will be used to estimate the denominator degrees of freedom. Type III tests for the least squares (LS) means will be used for the statistical comparison; the 95% CI will be reported. Treatment group comparisons at Week 12 (Visit 7) and all other post-baseline visits will be reported.

When the ANCOVA model is used, the model includes treatment, and baseline value with the last observation carried forward (LOCF) (Section 6.2.2). Type III sums of squares for the LS means will be used for the statistical comparison; the 95% CI will be reported.

For variables that are not collected at each post-baseline visit, data may exist at visits where the variable was not scheduled to be collected, due to early discontinuation visits. In these situations, data from the early discontinuation visit that does not correspond to the planned collection schedule will be excluded from the MMRM analyses. However, the data will still be used in other analyses, including shift analyses, change from baseline to LOCF endpoint analyses, and other categorical analyses.

Time to first clinical response (e.g. sPGA (0,1)) on initially assigned treatment will be assessed based on the ITT Population in Period 2. Unless otherwise specified, time to first clinical response (e.g. sPGA (0,1)) is defined as:

$$\text{Time to first clinical response (days)} = \text{Date of first clinical response during Period 2 on initially assigned treatment} - \text{Date of Week 0 randomization} + 1$$

If a patient has not met the criteria for response by completion or early discontinuation of Period 2 on initially assigned treatment, the patient will be censored at the date of their last visit during Period 2.

A Kaplan-Meier plot of the time to first clinical response by treatment group will be provided. The number of patients at risk and experiencing a response by each scheduled visit during Period 2 will be presented by treatment group. Treatment group comparisons will be performed using the log-rank test.

Fisher's exact test will be used for all adverse events (AEs), baseline characteristics, previous and concomitant therapy, treatment compliance, discontinuation, and other categorical safety data. The continuous baseline characteristics will be analyzed using an analysis of variance (ANOVA) model with treatment group as a factor. Continuous vital sign data and laboratory values will be analyzed by an ANCOVA with treatment and baseline value in the model where appropriate.

6.1.3. General Considerations for Analyses during Period 3 (Maintenance Dosing Period)

Period 3 starts at the first injection of study treatment at Week 12 (Visit 7) and ends on the date of Week 60 (Visit 19) or the date of the ETV (if it occurs between Weeks 12 and 60).

For Period 3 efficacy and health outcomes analyses, baseline is defined as the last non-missing assessment recorded on or prior to the date of first injection of study treatment at Week 0 (Visit 2). In most cases, this will be the measure recorded at Week 0 (Visit 2).

Unless otherwise specified, for Period 3 safety analyses, baseline and baseline period are defined as the last non-missing assessment prior to the first injection of study treatment at Week 12 (Visit 7). In most cases, this will be the measure recorded at Week 12 (Visit 7). For treatment-emergent adverse events, baseline is the event started prior to the study drug injection at Week 12 (Visit 7) and continued into Period 3.

For patients who met relapse criteria (loss of response; sPGA ≥ 3) and were retreated with ixekizumab, only data up to the time of relapse will be included in the maintenance of effect analyses. These patients will be considered non-responders to categorical assessments per the NRI imputation method (see Section 6.2.1).

6.1.3.1. Maintenance Dosing Period Primary Population

Unless otherwise specified, treatment comparisons of categorical efficacy and health outcomes variables will be analyzed using a logistic regression model with treatment group fitted as an explanatory variable. The odds ratio and the corresponding 95% CIs, as well as the treatment differences and the corresponding 95% CIs, will be reported. Secondary analysis on the categorical efficacy and health outcome variables will be conducted using a Fisher's exact test.

As a sensitivity analysis for selected categorical efficacy measures e.g. sPGA (0,1), sPGA (0), PASI 75/90/100, a categorical, pseudo-likelihood based mixed-effects model of repeated measures (categorical mixed-effects model of repeated measures [MMRM]) estimating the percentage of patients achieving response across postbaseline visits will be used. The model will include treatment, baseline value, visit, treatment-by-visit and baseline-by-visit interactions as fixed factors. The binomial distribution and the logit link function will be used. The restricted maximum likelihood (REML) will be used. An unstructured covariance matrix will be used to model the within-patient variance-covariance errors. The Kenward-Roger approximation will be used to estimate the denominator degrees of freedom. The Newton-Raphson with ridging optimization technique will be used to aid with convergence. The probability of response, the corresponding 2-sided 95% CI, and the p-value for treatment comparisons at Week 60 (Visit 19) and all other postbaseline visits will be reported.

Treatment comparisons for continuous efficacy and health outcomes variables will be made using MMRM models. ANCOVA models will also be used for selected continuous efficacy and health outcomes variables.

When MMRM is used, the model will include treatment, baseline value, visit, treatment-by-visit, and baseline-by-visit interactions as fixed factors. The covariance structure to model the within-patient errors will be unstructured. If the unstructured covariance matrix results in a lack of

convergence, the heterogeneous Toeplitz covariance structure, followed by the heterogeneous autoregressive covariance structure, followed by compound symmetry will be used. The Kenward-Roger method will be used to estimate the denominator degrees of freedom. Type III tests for the least-squares (LS) means will be used for the statistical comparison; the 95% CI will be reported. Treatment arm comparisons with placebo at Week 60 (Visit 19) and all other visits will be tested.

When the ANCOVA model is used, the model includes treatment and baseline value in the model. Type III sums of squares for the LS means will be used for the statistical comparison. For each treatment comparison performed, the LS mean for each treatment group, an estimate of the difference between treatments, corresponding 95% CI and p-value will be presented.

The time to relapse (loss of response; sPGA ≥ 3) during Period 3 is defined as:

$$\text{Time to relapse (days)} = \text{date of first sPGA} \geq 3 \text{ during Period 3} - \text{date of Week 12 re-randomization} + 1.$$

If a patient has not experienced relapse by completion or early discontinuation of Period 3, the patient will be censored at the date of their last visit during Period 3.

For each treatment group, a Kaplan-Meier plot of the time to relapse will be provided. The number of patients at risk and experiencing a relapse event by each scheduled visit during Period 3 will be presented by treatment group. Within each induction treatment group, maintenance treatment group comparisons will be performed using the log-rank test.

For the safety analyses, treatment group comparisons will be performed. Fisher's exact test will be used for all AE, baseline, discontinuation, and other categorical data. The continuous baseline characteristics will be analyzed using an ANOVA model with treatment as a factor. Continuous vital sign, and laboratory values will be analyzed by an ANCOVA model with treatment and baseline value as independent variables.

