5.3. Determination of Sample Size

The total sample size for the study is 420 patients randomized at a 2:2:1 ratio in the blinded Induction Dosing Period to 80 mg Q2W, 80 mg Q4W, and placebo, respectively. In order to account for multiple testing for the 2 ixekizumab groups, a 2-sided Fisher's exact test at the 0.025 level is assumed. Assuming the response rates for both sPGA (0,1) and PASI 75 at Week 12 (Visit 7) are 75% for each ixekizumab treatment group and 5% for the placebo group, 168 patients in 80 mg Q2W or 80 mg Q4W versus 84 patients in placebo group will provide >99% power to test the superiority of each ixekizumab dose regimen to placebo for sPGA (0,1) and for PASI 75. These assumptions are based on the integrated results from the pivotal Phase 3 Studies RHAZ, RHBA, and RHBC.

Assuming 70% of the ixekizumab patients are re-randomized in the Maintenance Dosing Period at Week 12 (Visit 7) at a 2:1 ratio to 80 mg Q4W or placebo, approximately 78 patients will be included in 80 mg Q4W group and 39 patients in placebo group. This sample size will:

- provide >99% power to test the difference in the proportion of patients maintaining sPGA (0, 1) from Week 12 (Visit 7) after re-randomization at start of Maintenance Dosing Period to Week 60 (Visit 19) in the Maintenance Dosing Period Primary population between the ixekizumab dosing interval and placebo within the original treatment group, assuming the proportions of patients maintaining sPGA (0, 1) are 70% for 80 mg Q4W and 10% for placebo within each original treatment group (Visit 19). A 2-sided Fisher's exact test at the 0.025 significance level is assumed.
- provide >99% power to test the difference in the proportion of patients maintaining a PASI 75 from Week 12 (Visit 7) after re-randomization at start of Maintenance Dosing Period to Week 60 (Visit 19) in the Maintenance Dosing Period Primary population

between the ixekizumab dosing interval and placebo within each original treatment group, assuming the proportions of patients maintaining a PASI 75 are 70% for 80 mg Q4W and 10% for placebo within each original treatment group. A 2-sided Fisher's exact test at the 0.025 significance level is assumed.

6. A Priori Statistical Methods

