6.1.1. Analysis Population

The following major analysis populations will be used (additional analysis populations for specific analysis will be defined in the corresponding analysis section):

Intent-to-Treat Population (ITT): Unless otherwise specified, efficacy and health outcomes analyses for Period 2 (Induction Dosing Period) will be conducted on the intent-to-treat (ITT) population, defined as all randomized patients, even if the patient does not take the assigned treatment, does not receive the correct treatment, or otherwise does not follow the protocol. Patients will be analyzed according to the treatment to which they are assigned.

Per Protocol Set (PPS): In addition, the primary analysis will be repeated using the per protocol set (PPS), which is defined as all randomized patients who are compliant with therapy, who do not have a subset of important protocol deviations that impact the primary efficacy endpoint (Section 6.5), and whose investigator site does not have significant good clinical practice (GCP) issues that require a report to the regulatory agencies prior to Week 12 (Visit 7). Compliance with therapy is defined to be missing no more than 20% of expected doses, not missing 2 consecutive doses, and no double dosing (that is, taking more injections at the same time point than specified in the protocol) during the period that patients participated in the study and prior to Week 12 (Visit 7) (see Section 6.8). Patients will be analyzed according to the treatment to which they are assigned.

Safety Population: Safety analyses for Period 2 will be conducted on the Safety Population, defined as all randomized patients who received at least 1 dose of study treatment. Patients will be analyzed according to the treatment to which they were assigned.

Maintenance Dosing Period Primary population: defined as all re-randomized patients (that is, patients randomized to ixekizumab in Period 2 who achieved an sPGA (0, 1) and were re-randomized at Week 12) who received at least 1 dose of study treatment during Period 3.

Patients will be analyzed according to the treatment to which they were re-randomized. Only information prior to relapse will be presented.

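### Pooled maintenance-period efficacy models leave out the re-randomisation stratum, and the continuous models ignore the Week 12 value: a low-priority precision point, with possible bias only in the pooled MMRM

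*SAP*

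**What the plan says.** **Randomisation.** Protocol 7.1.3 and 9.3 and SAP 5.2 re-randomise ixekizumab responders 2:1 to ixekizumab Q4W or placebo, stratified by induction regimen (Q2W or Q4W).

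**Pooled comparison.** SAP Table RHBH.6.1 adds a pooled IXE/IXE versus IXE/PBO comparison to the two within-regimen ones. Tables RHBH.6.5 and RHBH.6.7 apply it to most Period 3 efficacy and health-outcome variables. Joint pain VAS and time to relapse have no pooled comparison.

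**Models (SAP 6.1.3.1).** Binary outcomes are analysed "using a logistic regression model with treatment group fitted as an explanatory variable". For the categorical MMRM, "The model will include treatment, baseline value, visit, treatment-by-visit and baseline-by-visit interactions as fixed factors"; the continuous MMRM has the same list. For ANCOVA, "the model includes treatment and baseline value in the model". If the unstructured covariance does not converge, "the heterogeneous Toeplitz covariance structure, followed by the heterogeneous autoregressive covariance structure, followed by compound symmetry will be used". Regimen appears in none of these.

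**Baseline and data cut.** For Period 3 efficacy and health outcomes, "baseline is defined as the last non-missing assessment recorded on or prior to the date of first injection of study treatment at Week 0". Period 3 starts at the Week 12 injection, so the pre-dose Week 12 score is neither a covariate nor a response, although the protocol's Study Schedule collects it at Visit 7 for every scale concerned. Period 3 safety analyses do use a Week 12 baseline. For patients who relapse and are retreated, "only data up to the time of relapse will be included in the maintenance of effect analyses". SAP 6.1.1 says of the same population: "Only information prior to relapse will be presented".

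**Planning rates.** SAP 5.3 assumes that the proportions maintaining response "are 70% for 80 mg Q4W and 10% for placebo within each original treatment group", so it assumes no regimen effect.

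**The concern.** An analysis normally reflects the strata used to randomise, and a score measured just before randomisation is usually among the best available covariates. The pooled models use neither. There is some reason to expect regimen to matter: the supporting information in Protocol 9.4.2 reports better outcomes with Q2W than with Q4W in almost every subgroup, though it does not show this for maintenance after re-randomisation.

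Two things could be lost. One is precision. The other arises because the repeated-measures data stop at relapse. The strata are balanced at Week 12, but the placebo patients still contributing at Week 60 may come mainly from one regimen. A model without regimen cannot correct for that.

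**Working it through.** **1. The plan's own figure.** 420 × 2/5 = 168 per ixekizumab arm; 168 × 0.70 = 117.6 re-randomised per regimen; split 2:1 this gives 78.4 and 39.2, that is 78 versus 39. Exact two-sided Fisher power at 0.025 for 70% versus 10% is 0.999999, so the stated >99% is reproduced. This test is within regimen, so the stratum term is irrelevant to it. Pooled numbers are 156 versus 78.

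**2. Pooled risk difference.** Unstratified SE = √[p₁(1−p₁)/156 + p₀(1−p₀)/78] at the mean rates 70% and 10% = √(0.21/156 + 0.09/78) = 0.0500. Stratified SE = ½√[Σ over regimens of p₁(1−p₁)/78 + p₀(1−p₀)/39].

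| Active, by regimen | Placebo, by regimen | Unstratified | Stratified | Saving |
|---|---|---|---|---|
| 70/70 (plan) | 10/10 (plan) | 0.0500 | 0.0500 | 0% |
| 75/65 (assumed) | 15/5 (assumed) | 0.0500 | 0.0495 | 1% |
| 80/60 (assumed) | 15/5 (assumed) | 0.0500 | 0.0490 | 2% |

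Allocation is 2:1 in both strata and NRI keeps every patient in the denominator, so the risk difference itself is unbiased.

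**3. Pooled logistic model.** Take a common odds ratio with active rates 75/65 and placebo rates 12.1/7.9. The unadjusted odds ratio is (0.7/0.3)/(0.1/0.9) = 21.0; conditional on regimen it is 21.7. The SE of the log odds ratio is 0.416 versus 0.420, and z is 7.32 versus 7.34. The SE does not fall; the estimate moves because odds ratios do not average across strata.

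**4. Size of the unadjusted pooled Wald test.** At nominal 0.05, with no treatment effect and a mean rate of 70%, simulated size is 0.0486, 0.0471 and 0.0434 at regimen gaps of 0, 10 and 20 points. At a mean rate of 50% it is 0.0464, 0.0460 and 0.0424. The test is conservative.

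**5. Pooled MMRM with data cut at relapse.** Generalised least squares with known covariance, 156 versus 78, 12 visits, true treatment effect zero, Monte Carlo error about 0.01 SD. Assumed Week 60 retention is 85% on active, and 10% and 35% on placebo in the two regimens (about 4 and 14 of 39). Week 60 bias in SD units:

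| Assumed regimen effect over time | No regimen term | Single regimen term | Regimen-by-visit |
|---|---|---|---|
| Fades from 0.6 SD to 0 | 0.07 | 0.12 | 0.01 |
| Grows from 0 to 0.6 SD | −0.13 | −0.10 | 0.01 |

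With equal placebo retention in the two regimens the three models agree and the bias is about zero. With complete data the omission costs only precision: the SE ratio is 1/√(1 + d²/4), a saving of 0.5% for a regimen difference of d = 0.2 SD and 3.0% for 0.5 SD.

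**6. Week 12 value.** The documents give no correlation ρ between the Week 12 value and the Week 60 outcome, so a range is shown for 78 versus 39.

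| SE saving | ρ = 0.15 | ρ = 0.3 | ρ = 0.5 |
|---|---|---|---|
| Week 60 MMRM, Week 12-by-visit added | −0.6 to 0.3% | 0.5 to 2.6% | 3.5 to 8.4% |
| ANCOVA, every patient with an endpoint | 0.8% | 4.4% | 13.1% |
| ANCOVA, subset of 31 versus 16 | −0.2% | 3.6% | 12.2% |

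The MMRM row assumes a separate model per regimen, with 85% of active and 15 to 30% of placebo patients still observed at Week 60 (6 to 12 of 39). The ANCOVA rows follow √(1−ρ²), less a small cost for the extra parameter. All re-randomised patients have sPGA 0 or 1 at Week 12, which restricts PASI and BSA and favours low ρ for them: about nil to 2% in the Week 60 MMRM. In a stress run where placebo dropout depended strongly on a strongly prognostic Week 12 value, omitting it left a bias of 0.024 on an effect of 2.00, about 1%.

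**The case against.** The strongest reply is that nothing important depends on this. Gatekept Tests 6 and 7 are within regimen, where the stratum is constant, and the other eight are Week 12 tests, for which Week 0 is the right baseline. The relapse log-rank test is also within regimen. Pooling is a SAP addition that does not appear in Protocol Table RHBH.12.1, and SAP 6.3 gives it no multiplicity control. The precision gain is nil under the planning rates and small otherwise. The bias needs large regimen differences in both outcome and retention. Every correlation and retention figure is assumed. Adding regimen replaces a marginal odds ratio with a conditional one, and extra visit interactions strain a model whose unstructured covariance already has 78 parameters at 12 visits. SAP 6.1.3.1 also does not say whether the within-regimen contrasts come from separate models or from one four-group model, so the Week 12 figures rest on one reading.

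All of this stands, and it sets the priority. It does not show that the omission is right. The terms cost almost nothing, the relapse test in the same section already respects the strata, and the safety ANCOVA already adjusts for the Week 12 value.

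**Conclusion.** The omission is real and its consequences are small. For pooled binary outcomes with NRI it costs 0% to 2% in precision. For the pooled MMRM, freedom from bias is conditional: it needs either no regimen effect on outcome or similar retention by regimen. The 0.07 to 0.13 SD range is an extreme case, not an expectation. The Week 12 value matters mainly for ANCOVA with LOCF, and only if its correlation with the outcome is moderate or higher.

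Four stronger readings are not supported:

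- A reader might infer from SAP Table RHBH.6.5, which lists the pooled comparison in rows labelled major secondary, that a confirmatory result is affected. SAP 6.3 defines Tests 6 and 7 within regimen only.
- A reader might infer inflated type I error in the pooled binary test. It is slightly conservative.
- A reader might infer that measuring change from Week 0 is an error. The objectives define change from baseline, and that outcome should stay; only the covariates are in question.
- A reader might infer that a stratum balanced at randomisation can never cause bias. That holds for the NRI risk difference but not for a repeated-measures model cut at relapse.

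Priority: low (optional).

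**What to change.** In SAP 6.1.3.1:

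- **(a) Pooled comparisons only.** Add induction regimen to the logistic and ANCOVA models. Add regimen and regimen-by-visit to the MMRM, and to the categorical MMRM if it converges. A single regimen term in the MMRM is not enough: in one of the two cases in step 5 it made the bias worse. Report the risk difference stratified by regimen with Mantel-Haenszel weights, and label the adjusted odds ratio as conditional on regimen.
- **(b) Week 12 value.** Add it to the Period 3 ANCOVA with LOCF for PASI, DLQI and NAPSI. For endpoints analysed in all re-randomised patients, add a labelled supportive MMRM with Week 12 and Week 12-by-visit. Make no Week 12 change to the planned MMRM, so that no covariate has to be dropped in response to the data.
- **(c) Missing Week 12 scores.** Fill them with the last value before re-randomisation, so that no patient is lost.

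Keep change from Week 0 as the outcome. Protocol 12.2.1.2 lists the same model terms, so under SAP 6.1 the change and its justification belong in the clinical study report. If treatment codes are already open, report all of this as labelled supportive analyses.

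**Cost.** SAP wording and no new data. Regimen with regimen-by-visit adds at most 12 parameters to the pooled MMRM (1 + 11 at 12 visits), with some convergence risk. The Week 12 value adds one parameter to each ANCOVA. The pooled odds ratio becomes conditional rather than marginal.
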